## **10. DISCONTINUATION OF STUDY TREATMENT AND WITHDRAWAL OF SUBJECTS FROM THE STUDY**

Subjects must be withdrawn from the treatment and the study for any one of the following reasons:

- The subject withdraws consent or the parent or legally authorized representative (e.g., parent or legal guardian) withdraws consent on behalf of the subject.
- The subject is unwilling or unable to comply with the protocol.
- The subject enrolls into another interventional clinical study in which an investigational treatment or approved therapy for investigational use is administered.
- ITI treatment is interrupted for >2 weeks.
- Emergent or elective surgery. Minor surgery such as tooth extraction or insertion/replacement of central venous access device is not a criterion for withdrawal.
- The subject received concomitant immunomodulation.
- The subject uses FVIII products other than rFVIIIFc (exception allowed for 1 emergency or accidental use).
- If, in the clinical judgment of the Investigator or Sponsor, it is not in the subject's best interest to continue with the study treatment.

The reason for the subject's withdrawal from the study must be recorded in the subject's electronic case report form (eCRF). When a subject is withdrawn, the date of study treatment dose and the date and reason for treatment/study withdrawal (see above) will be clearly described in the relevant sections of the eCRF. If a subject is removed from treatment because of an AE, the reason for treatment withdrawal will be stated as "adverse event" irrespective of whether this was the Investigator's or the subject's decision. This subject will be followed until the event has resolved, stabilized, or returned to baseline.

The withdrawn subject will be examined as soon as possible, whenever possible, irrespective of the reason for withdrawal. Subjects who are withdrawn will not be replaced. Relevant samples will be obtained, and all relevant assessments will be completed, preferably according to the schedule for EOT Visit. The eCRF will be completed as much as possible.

CONFIDENTIAL

The information contained herein may not be used, disclosed, or published without the written consent of  
Bioverativ Therapeutics Inc.

Page 50

VV-CLIN-0542000 3.0

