### 6.2. Secondary Objectives and Endpoints

The secondary objectives are as follows:

- To describe the outcome of ITI treatment
- To describe the relapse rate over the 48-week (12-month) period following successful ITI performed with rFVIIIFc
- To describe the intercurrent bleeding during the ITI Period and during the 48-week (12-month) period after successful ITI performed with rFVIIIFc
- To describe the safety and tolerability of rFVIIIFc when used for ITI
- To evaluate the impact of ITI treatment with rFVIIIFc on health economics and adherence

The secondary endpoints are as follows:

- ITI success
  - Confirmed negative titers consisting of 2 consecutive negative inhibitor assessments within 2 weeks ( $\pm 3$  days) based on local laboratory results  $<0.6$  BU/mL by the Nijmegen-modified Bethesda assay; determination of negative titer based on the Bethesda assay is acceptable at sites that have not yet adopted the Nijmegen-modified Bethesda assay
  - IR  $\geq 1.32$  IU/dL per IU/kg in 2 consecutive assessments representing  $\geq 66\%$  of the expected IR 2 IU/dL per IU/kg ([SmPC](#); [USPI](#))
  - $t_{1/2} \geq 7$  hours
- Occurrence of relapse (defined as confirmed positive inhibitor titer  $\geq 0.6$  BU/mL), abnormal recovery after tolerance is achieved, and  $t_{1/2} < 7$  hours) during the Tapering or Follow-Up Periods
- Number of bleeding episodes during the ITI Period and during the 48-week (12-month) period after successful ITI performed with rFVIIIFc
- Adverse events (AEs) and serious adverse events (SAEs)

[figure not shown]
CONFIDENTIAL

The information contained herein may not be used, disclosed, or published without the written consent of  
Bioverativ Therapeutics Inc.

Page 36

- Number of days away from work or school
- Number of hospitalization days
- Adherence (defined as percentage of administered doses versus planned doses)
- Consumption of rFVIIIFc (measured in total rFVIIIFc use)

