#### Occurrence of relapse after successful ITI

Occurrence of relapse will be summarized descriptively by calculating the proportion of subjects with ITI success who reach the criteria for relapse. The TPFAS will be used for this analysis.

Time to relapse will be defined as the duration between ITI success and time of relapse. Time to relapse from successful ITI will also be summarized descriptively for subjects who relapsed during the Tapering or Follow-Up Period.

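### Tolerized subjects withdrawn under Section 10 before Week 48 are in effect scored as not relapsed, so the 48-week relapse proportion is biased downward

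*Protocol*

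**What the plan says.** Protocol Section 10 introduces its list with "Subjects must be withdrawn from the treatment and the study for any one of the following reasons". The triggers include:

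- surgery: "Emergent or elective surgery. Minor surgery such as tooth extraction or insertion/replacement of central venous access device is not a criterion for withdrawal"
- immunomodulation: "The subject received concomitant immunomodulation"
- other factor products: "The subject uses FVIII products other than rFVIIIFc (exception allowed for 1 emergency or accidental use"
- a judgment by the investigator or sponsor that continuing is not in the subject's interest.

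Only the bullet on treatment interruption of more than two weeks is tied to ITI treatment. The others carry no period limit. A withdrawn subject is examined once, if possible: "Relevant samples will be obtained, and all relevant assessments will be completed, preferably according to the schedule for EOT Visit". Nothing further is scheduled except follow-up of an adverse event that caused the removal.

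The relevant secondary objective in Section 6.2 is "To describe the relapse rate over the 48-week (12-month) period following successful ITI performed with rFVIIIFc". Section 16.2.2.2 gives the analysis: "Occurrence of relapse will be summarized descriptively by calculating the proportion of subjects with ITI success who reach the criteria for relapse". The analysis set is the TPFAS, which is everyone who enters tapering. SAP 4.4.1.2 repeats this by period and for both periods combined, and summarizes time to relapse in relapsers only.

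Under Section 7.2.4, relapse needs a positive titer and a low IR, each on two consecutive assessments 2 to 4 weeks apart. SAP 4.4.1.1 likewise requires a confirmed positive titer together with low IR.

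**The concern.** Stopping study drug and stopping observation are treated as one event. After ITI success, observation is what the relapse endpoint depends on. A tolerized subject removed at, say, Week 16 contributes nothing to the numerator for the remaining 32 weeks but counts fully in the denominator.

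Neither document has a category for him. The outcome-not-determinable category in Protocol Section 7.2.2.2 and SAP 4.4.1.1 covers withdrawal during the ITI Period only. SAP 1.2.1 marks estimands as not applicable, and no sensitivity analysis is planned for relapse. At stake is whether the reported proportion answers the 48-week objective. Titers that were never drawn cannot be recovered at analysis.

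**Working it through.** The documents state no relapse rate, withdrawal rate or precision target, so there is no planned figure to reproduce. The check is one of logic, then of bounds, then of expected size under stated assumptions.

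**1. Can a relapse still be confirmed after the trigger?** In Protocol Table 2 the EOT Visit includes the inhibitor assay and half-life sampling. Table 2 footnote 11 and Section 13.1.2.1 say IR is determined from those same samples. So:

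- A subject with a positive titer and low IR 2 to 4 weeks before exit can be confirmed at exit, if the EOT schedule is followed.
- A subject with no earlier signal has at most one assessment, and relapse needs two. He cannot be confirmed.

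**2. How is the second subject scored?** No sentence calls him relapse-free. The result follows from a numerator of confirmed relapses over a denominator of all who entered tapering.

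**3. Bounds.** Let *m* be the number tolerized, *w* those leaving before Week 48 without confirmed relapse, and *r* the confirmed relapses.

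- Planned estimate: r/m
- Among known status: r/(m − w)
- Upper bound: (r + w)/m

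For *m*, take 17 subjects (Protocol Section 16.1) and the published success range of 33% to 88% (Section 5.1): 17 × 0.33 = 5.6 and 17 × 0.88 = 15.0, so about 6 to 15. Each withdrawal leaves 1/m undetermined, from 1/15 = 6.7 to 1/6 = 16.7 points.

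| m | r | w | Planned | Known status | Upper bound |
|---|---|---|---|---|---|
| 6 | 1 | 2 | 1/6 = 16.7% | 1/4 = 25.0% | 3/6 = 50.0% |
| 15 | 1 | 2 | 1/15 = 6.7% | 1/13 = 7.7% | 3/15 = 20.0% |

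SAP Section 2 gives up to 30 patients, although the SAP says it is based on the protocol version that plans 17. The two need reconciling. With 30, *m* is about 10 to 26 and each withdrawal leaves 1/26 = 3.8 to 1/10 = 10 points open.

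**4. Expected size if removal is unrelated to relapse.** Assume a true 48-week risk *q*, constant hazard, a share *d* removed at Week 16, and no relapse recorded after removal. Then

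expected reported proportion = (1 − d) × q + d × [1 − (1 − q)^(16/48)].

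For q = 20% the bracket is 1 − 0.8^(1/3) = 0.0717. With d = 10% this gives 0.9 × 0.20 + 0.1 × 0.0717 = 0.187.

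| True 48-week risk | d = 10% | d = 20% | d = 30% |
|---|---|---|---|
| 10% | 9.3% | 8.7% | 8.0% |
| 20% | 18.7% | 17.4% | 16.2% |
| 30% | 28.1% | 26.2% | 24.4% |

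Every entry lies below the true value. *q*, *d* and the Week 16 timing are assumptions, not document figures.

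**The case against.** **The plan already shows these subjects.** SAP 4.2 lists duration, last visit and reason for every non-completer. SAP 4.3.4 lists relapse status and time in each period by patient. With so few subjects a reader could build the bounds by hand. That stands in part: the cases are visible, but the headline proportion still scores them as no relapse.

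**SAP 4.1 has a general censoring rule.** It provides Kaplan-Meier estimates with censoring at the last on-study visit. But it names the ITIFAS, which includes subjects never tolerized, and the relapse section does not take it up. It would not change the planned proportion, and censoring would itself assume that removal is unrelated to relapse.

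**Later titers may not serve the endpoint.** Relapse also needs low rFVIIIFc IR, so a subject no longer given rFVIIIFc cannot meet the definition. This stands, and it shapes the fix.

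**The study is small and descriptive.** The exact 95% interval for 1 relapse in 8 is about 0.3% to 53%, far wider than the bias. True, but sampling error has no fixed direction, and this bias does.

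**Stronger readings.** A reader might infer that a removed subject can never be confirmed unless he already was; step 1 of the working shows that the exit visit can supply the second assessment. A reader might also infer that the rule cuts observation in those most likely to relapse. Support for that is partial. Section 5.1 notes that some ITI regimens add immunomodulation, and Section 5.2.3 cites a patient switched between FVIII products while his titer rose. Nothing ties surgery to relapse, and planned major surgery is excluded at entry. For bleeds after success, Sections 7.2.4 and 7.2.5 call for inhibitor testing and allow bypassing agents, which are not a withdrawal trigger.

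**Conclusion.** The concern holds, within limits. Section 10 ends observation along with treatment. With a confirmed-only numerator and an all-entrants denominator, any relapse that would have emerged after removal is lost, and the 48-week proportion is biased downward. Minor surgery and a single emergency or accidental use of another FVIII do not trigger removal.

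The size cannot be fixed from the documents. Each withdrawal leaves about 7 to 17 points undetermined at 6 to 15 tolerized subjects. Under uninformative removal of 10% to 30% at Week 16, a true 20% is reported as about 16% to 19%. The understatement is larger if the trigger is linked to a returning inhibitor. One can reach 3 to 14 points by assuming a 30% to 50% relapse risk in one or two removed subjects among 7 to 10 successes, with none of that risk observed before exit (1 × 0.30/10 to 2 × 0.50/7). The documents support none of those inputs, so that range should not be read as an estimate.

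This is a secondary endpoint in an uncontrolled study without hypothesis testing. The change is a cheap improvement, not a condition for the study's validity.

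**What to change.** 1. **SAP 4.4.1.2.** Report tolerized subjects who leave before Week 48 without confirmed relapse, for any reason, as 48-week status unknown, with the reason and the last titer and IR. Give the relapse proportion twice, counting them first as no relapse and then as relapse, and present the pair as bounds. The cost is one paragraph and one table row.

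2. **Protocol Section 10.** Leave every criterion for stopping treatment as it is. For subjects who have reached ITI success, separate stopping rFVIIIFc from leaving the study. Unless consent is withdrawn, continue inhibitor titers at the Table 2 visits to Week 48, with IR only where rFVIIIFc is still given, and record the trigger. Report confirmed positive titers after stopping or switching product separately, flagged with the trigger, and not as protocol-defined relapse.

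The second change needs an amendment and a few extra titer visits, probably for one or two subjects. Titers after a product switch or immunomodulation are harder to interpret, hence the flag. If an amendment is no longer practical, the first change is still worth making on its own.

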## 11. STUDY TREATMENT

The Sponsor will provide rFVIIIFc to sites in all countries.

### 11.1. Dosing Regimen and Administration

Refer to and follow the package insert or the Directions for Handling and Administration (DHA). See Section 5.4 for the rationale for the selected dosage regimen, dose levels, and treatment duration.

During the ITI Period, the rFVIIIFc dose administered is 200 IU/kg/day ( $\pm 8$  hours), which may be given as a once-daily dose or divided into several doses per day. If FVIII activity levels rise above 200 IU/dL, after the inhibitors are negative but before all of the ITI success criteria are met, the dose will be adjusted according to Investigator judgment to maintain the FVIII activity levels between 100 and 200 IU/dL (see Table 4).

During the Tapering Period (with all 3 tolerization success criteria met), the rFVIIIFc dose administered will be adjusted according to Investigator judgment based on the FVIII activity levels to maintain the FVIII activity levels between 100 and 200 IU/dL during the initial part of the Tapering Period, with the aim of tapering the rFVIIIFc dose to reach a prophylactic dosing regimen within 16 weeks (4 months).

An example of a dose adjustment schedule after the inhibitor titer has become negative and the subject has not met all the criteria for a successful tolerization is shown in Table 4. The dose adjustment will be individualized according to each subject's FVIII activity levels during this period.

**Table 4 Example of a Dose Adjustment Schedule: Negative Inhibitor, Not All Success Criteria Met**

Peak FVIII Activity Levels	Dose of rFVIIIFc per Day
<200 IU/dL	200 IU/kg/day
$\geq 200$ IU/dL	100 IU/kg/day

Abbreviations: FVIII=coagulation factor VIII; rFVIIIFc=recombinant coagulation factor VIII Fc fusion protein.

During the Tapering Period (with all 3 tolerization success criteria met), the aim is to keep FVIII activity levels approximately between 100 and 200 IU/dL for at least 4 weeks (1 month), with the aim of tapering the dose to reach the prophylactic dosing regimen within at least 12 weeks (3 months) (see Table 5). It is recommended that the entire Tapering Period be at least 16 weeks (4 months). This schedule is only an example, and each subject's tapering schedule is left to the treating physician's discretion.

CONFIDENTIAL

The information contained herein may not be used, disclosed, or published without the written consent of Bioverativ Therapeutics Inc.

Page 51

**Table 5 Example of a Dose Tapering Schedule: All 3 Success Criteria Met**

Tapering Period	Dose and Interval
Weeks 1 to 6	100 IU/kg QD
Weeks 6 to 12	100 IU/kg QOD
Weeks 12 to 16	50 IU/kg QOD
Week 16 onward	50 IU/kg 3 times per week (prophylaxis)

Abbreviations: QD=once a day; QOD=every other day.

During the Follow-Up Period, the prophylaxis regimen will be adjusted based on clinical response and with the goal of keeping FVIII activity levels  $\geq 1$  IU/dL at all time points according to Investigator judgment and local practice.

If the subject misses a dose, the Investigator should be notified, and the Investigator will determine when the next dose of rFVIIIFc should be taken.

Bleeding episodes occurring during the study will be treated per Investigator judgment and within labeled dosing recommendations. Concomitant treatment with bypassing agents such as aPCC (FEIBA) or rFVIIa (NovoSeven) will be allowed during the ITI Period under certain circumstances (see Section 7.2.2.1 for details).

### **11.1.1. Administration of rFVIIIFc**

After dissolving the powder for injection with the solvent supplied in the pre-filled syringe, rFVIIIFc will be delivered via a slow push intravenous (IV) injection over several minutes, at a rate of administration determined by the subject's comfort level.

Because of the risk of allergic reactions with FVIII concentrates, the initial administration of rFVIIIFc will be performed under medical observation, where proper medical care for allergic reactions could be provided. Subjects/caregivers will be instructed to administer subsequent rFVIIIFc doses at home, except for the dose given prior to assessments of rFVIIIFc  $t_{1/2}$  and IR, which will be administered in the clinic.

It is recommended that the subject/caregiver enter dosing information on rFVIIIFc and/or FVIII bypassing agents into the EPD immediately after an injection or within a maximum of 7 days, to ensure data integrity and to facilitate appropriate medical review and dosing guidance. Complete instructions for the preparation and administration of rFVIIIFc are provided in the DHA within the Study Reference Manual.

### **11.1.2. Calculation and Recording of Dosing Based on Actual Potency and Dosing Based on Nominal Strength**

Actual potency dosing is required for the dose of 50 IU/kg used to measure IR and  $t_{1/2}$  during the study. The actual potency shown on the vial must be used to calculate the units of rFVIIIFc and the volume to inject.

CONFIDENTIAL

The information contained herein may not be used, disclosed, or published without the written consent of Bioverativ Therapeutics Inc.

Note: The instructions and worksheets provided in the DHA must be used to calculate the volume for administration based on actual potency. The actual potency shown on the vial must be used to calculate the volume for administration.

The nominal strength is defined as the target potency of the vial (i.e., 250, 500, 1000, 2000, or 3000 IU per vial). Nominal strength will be used for all other rFVIIIFc dose calculations, and whole vials will be used to achieve the target dose, rounded to the nearest 250 IU.

### **11.1.3. Prior and Concomitant Therapy**

A concomitant therapy is any drug or substance administered from 30 days prior to the Screening Visit through the Final Safety Follow-Up Visit. Bypassing agents used during the study are considered concomitant therapy and should be recorded as such. For subjects who are receiving breast milk, any drug or substance being administered to the mother during the period when she is breastfeeding will also be considered a concomitant medication. Maternal concomitant medications will also be collected, unless the breast milk is derived from a source other than the mother. Maternal concomitant medications will no longer be collected after the discontinuation of breastfeeding.

The subjects or caregivers will be instructed that the subject should not start any new medications, including nonprescription drugs and herbal preparations, unless they have received permission from the Investigator.

### **11.1.4. Allowed Concomitant Therapy**

Therapy considered necessary for the subject's welfare, including routine immunizations, may be given at the discretion of the Investigator. Bypassing agents (e.g., aPCC [FEIBA] or rFVIIa [NovoSeven]) are allowed in subjects as outlined in Section 7.2.2.1. All such therapy must be recorded in the eCRF. The prophylactic use of bypassing agents in subjects requires discussion with the Sponsor Medical Monitor and documentation of rationale.

## **11.2. Compliance**

Compliance with treatment dosing is to be monitored and recorded by site staff.

The date and time of the rFVIIIFc administrations on Day 1 and the doses given prior to assessments of rFVIIIFc  $t_{1/2}$  and IR, which will be administered in the clinic, will be recorded in the eCRF. The date, time, amount of, and reason for rFVIIIFc administrations done outside the clinic will be recorded by the subject/caregiver in the EPD. The EPD data will be reviewed on an ongoing basis by study site staff and the Clinical Monitor.

## **11.3. Excluded Concomitant Therapies and Procedures**

A concomitant procedure is any therapeutic intervention (e.g., surgery/biopsy, physical therapy) or diagnostic assessment (e.g., blood gas measurement, bacterial cultures) performed from 30 days prior to the Screening Visit until the Final Safety Follow-Up Visit/Telephone Call. The reason for all concomitant procedures performed during the study will be documented in the medical records and recorded in the eCRF. AEs related to administration of these procedures must be documented on the appropriate eCRF.

CONFIDENTIAL

The information contained herein may not be used, disclosed, or published without the written consent of Bioverativ Therapeutics Inc.

Page 53

No other drug under investigation may be used concomitantly with the study treatment. Subjects are not allowed to participate concurrently in another interventional clinical study.

The following concomitant medications are not permitted during the study:

- Acetylsalicylic acid
- Current systemic treatment with chemotherapy and/or other immunosuppressant drugs. Use of corticosteroids for the treatment of asthma or management of acute allergic episodes is allowed with the exception of systemic corticosteroid treatment given to children daily or on alternate days at  $\geq 2$  mg/kg per day of prednisone or its equivalent or  $\geq 20$  mg/day if the duration is longer than 14 days.
- Concomitant immunomodulation will not be allowed during the study.
- Emicizumab® (Hemlibra)
- Any other FVIII

During the Tapering Period, treatment with bypassing agents may be considered if bleeding is unresponsive to treatment with rFVIIIFc (see Section 7.2.3). It is recommended that subjects be tested for inhibitors. See Section 7.2.2.1 for additional details regarding use of bypassing agents.

Subjects will be instructed to contact their Investigators before taking any new medications, including nonprescription drugs and herbal preparations.

CONFIDENTIAL

The information contained herein may not be used, disclosed, or published without the written consent of  
Bioverativ Therapeutics Inc.

Page 54

VV-CLIN-0542000 3.0

## **12. STUDY TREATMENT MANAGEMENT**

### **12.1. rFVIIIFc Stability and Storage**

rFVIIIFc is supplied in kits comprising a single-use vial containing nominally 250, 500, 1000, 2000, or 3000 IU of factor VIII potency, a pre-filled syringe with 3 mL of sterile water for injection, and a sterile vial adapter (reconstitution device). The actual amount of rFVIIIFc in IU is stated on the label and carton of each vial. Any of the potencies listed may be used. The label will include conditions for storage, lot number, and other pertinent information such as Sponsor and caution statement.

Study treatment must be stored in a secure location. Accountability for study treatment is the responsibility of the Investigator. More details concerning this responsibility are included in Section 12.2.

Study treatment must only be dispensed by a Pharmacist or a medically qualified staff. Study treatment is to be dispensed only to a subject (or subject's legally authorized representative) enrolled in this study. Once study treatment is prepared for a subject, it can only be administered to that subject. Study treatment vials are for 1-time use only; any study treatment remaining in the vial cannot be used for another subject.

Study site staff will refer to the approved package insert and DHA for specific instructions on the handling, preparation, administration, and disposal of the study treatment.

